# 1. Protocol Synopsis

Protocol Number:	SCR-005
Title:	Assessment of the Human Systemic Absorption of Sunscreen Ingredients
Investigators:	Principal Investigator: [name]
Study Phase:	1
Study Period:	This will be a single clinical study conducted in 2 parts. The duration of study participation will be approximately 37 days for part 1, including a 30-day screening period, a 4-day treatment period (Days 1-4) and subjects leaving the clinic on the morning of Day 7 following completion of scheduled End-of-Study activities. For part 2, the duration of participation will be approximately 51 days, including a 30-day screening period, a 4-day treatment period (Days 1-4) and subjects leaving the clinic on the morning of Day 7. Subjects in part 2 will then return to the clinical for follow-up visits on Days 10, 14 and 21 after which End-of-Study activities will be completed.
Study Site:	Spaulding Clinical Research LLC, [name]
Background and Motivation:	Sunscreens prevent skin damage by reflecting or absorbing ultraviolet (UV) radiation and they are regulated as drug products in the United States (U.S.). Most active ingredients in sunscreens are organic chemicals and some have been shown to be absorbed through human skin with detectable levels in the blood or urine. As part of the safety evaluation for sunscreen products, the Food and Drug Administration (FDA) requests an assessment of systemic absorption in humans so that human blood levels can be compared with exposure levels obtained in nonclinical toxicology studies. If testing establishes that the sunscreen is not absorbed through the skin into the body, some aspects of toxicology testing may not be needed. Sunscreen products may be applied multiple times daily as both primary sunscreen products and as ingredients in cosmetic products, in substantial amounts for a lifetime starting at 6 months of age. The amount of sunscreen ingredient in a product can vary, but permitted levels can be as high as 15% for some organic active ingredients and application to the skin can accumulate to gram quantities in a day even with modest use. Because of the significant use of these sunscreens, even a low percentage of systemic absorption (e.g., 0.1%) could represent a significant systemic exposure in a single day and over a lifetime.  The Surgeon General's Call to Action to Prevent Skin Cancer calls on partners in prevention from various sectors across the nation to address skin cancer as a major public health problem by increasing awareness of skin cancer and promoting actions to reduce its risk. Given the recognized public health benefits of sunscreen use, the

FDA is committed to finding ways to facilitate the marketing of sunscreen products that include additional over-the-counter (OTC) sunscreen active ingredients. The FDA will continue to work with industry and other public health agencies to ensure that the sunscreens consumers use are safe and effective for daily, life-long use.

In November 2016, the U.S. FDA finalized the guidance titled "Guidance for Industry: Nonprescription Sunscreen Drug Products Safety and Effectiveness Data" (sunscreen guidance). The guidance requests an assessment of the human systemic absorption of sunscreen ingredients with a Maximum Usage Trial (MUsT). The FDA sunscreen guidance notes that some nonclinical toxicity studies may be waived if results of an adequately conducted human pharmacokinetic (PK) MUsT show a steady-state blood level less than 0.5 ng/mL.

Periodically, the FDA performs testing of products and formulations that the Agency sees as important for public health. This testing is not a reflection of rulemaking or other regulatory actions, but instead is done independently to measure the agency's understanding of the products' overall safety and effectiveness.

This study is not intended to meet all requirements of MUsT studies as outlined in the FDA guidance referenced above, but will follow many of the principles.

# Summary and Objectives:

Part 1 is an open-label, randomized, 4-arm study in 24 healthy adult subjects with the primary objective:

• To explore whether the active components (avobenzone, oxybenzone, ecamsule and octocrylene) of 4 sunscreen products (1 sunscreen product in each arm) are absorbed into the systemic circulation when a sunscreen product is applied under maximal-use conditions.

One sunscreen product with the highest avobenzone exposure will be selected for the second part of the study. If there is no quantifiable exposure of avobenzone for any of the sunscreen products, the formulation with the highest oxybenzone exposure will be selected for Part 2. In addition, 3 new sunscreen products are being included in Part 2.

Part 2 is an open-label, 4-arm study in 48 healthy adult subjects with the following primary objective:

• To assess the systemic absorption and pharmacokinetics of the active components (avobenzone, oxybenzone, octocrylene, ecamsule, homosalate, octisalate and octinoxate, where applicable [Part 2 products will not contain ecamsule]) of 4 sunscreen products (1 sunscreen product in each arm) under maximal-use conditions.

### Study Design: Part 1

Part 1 is an open-label, randomized, 4-arm pilot study to evaluate the effects of multiple applications of 4 different topical sunscreen formulations in healthy adult subjects. Each arm will include 6 subjects (3 male and 3 female) with 1 formulation. A total of 24 subjects (12 male and 12 female) from all 4 arms will be admitted to the clinical research unit (CRU) on Day 0. On the morning of Days 1 through 4, subjects will receive a topical application of the study drug at approximately 0900 hours. The study product will be weighed in advance and applied by a qualified person from the study team. Subjects will then receive 3 more topical applications on the

same day at 2, 4, and 6 hours after the first dose.

#### Part 2

Part 2 is an open-label, 4-arm study to evaluate the pharmacokinetics of avobenzone, oxybenzone, octocrylene, homosalate, octisalate and octinoxate (where applicable [Part 2 products will not contain ecamsule]) after multiple applications of a topical sunscreen formulation in healthy adult subjects. Part 2 will include 48 subjects (24 male and 24 female) and each arm will include 12 subjects (6 male and 6 female). One of the formulations in Part 2 will be selected based on the plasma exposure data from the pilot study (Part 1) along with 3 additional formulations. A total of 48 subjects (24 male and 24 female) will be admitted to the CRU on Day 0. On the morning of Days 1 through 4, subjects will receive a topical application of the study product at approximately 0900 hours. The study drug will be weighed in advance and applied by a qualified person from the study team. Subjects will only receive one application on Day 1. On Days 2, 3 and 4, subjects will receive an initial dose and 3 more topical applications on the same day at 2, 4, and 6 hours after the first dose.

### Parts 1 and 2

In both parts, approximately 2 mg of active sunscreen ingredient per 1 cm^2 of body surface (calculation per method of Dubois) will be evenly applied 4 times per study day (except for a one-time application on the first day in part 2) to areas of the body typically exposed to the sun: face, ears, neck, torso, arms, and legs (approximately 75% of the body surface area). The antecubital areas will be avoided when applying the sunscreen due to potential contamination of the sites used for intravenous PK blood sample collection. The topical applications of study drug will be administered with subjects in swim wear to simulate real-world settings as well as for easy application. In addition to swim wear, subjects may wear scrubs in between applications and at other times throughout the day/night. Subjects are required to shower each morning after the first PK blood sample collection (and before the first dose of the day), but not at other times during the day.

Blood samples (approximately 10 mL per sample) will be collected for determination of plasma concentrations for all active ingredients (avobenzone, oxybenzone, octocrylene, ecamsule, homosalate, octisalate and octinoxate, where applicable).

Safety evaluations will include adverse event (AE) monitoring, vital sign measurements, and physical examinations. All AEs reported by the subject or observed by the investigator or clinical research unit (CRU) staff will be recorded. Any AE reported after the informed consent is signed and before study drug application will be recorded as medical history.

Subjects will remain in the CRU after admission on Day 0 until the morning of Day 7 following completion of scheduled End-of-Study activities for part 1. For part 2, subjects will undergo the same

	schedule but will return to the clinic for follow-up visits on Days 10, 14 and 21. Subjects will then be discharged following completion of End-of-Study activities.
	Subjects are not allowed to use products containing any of these active ingredients from 7 days before check-in until completion of End-of-Study procedures.
Inclusion Criteria:	Subjects who meet all of the following inclusion criteria will be eligible to participate in the study:
	1. Subject signs an IRB-approved written informed consent and privacy language as per national regulations (e.g., Health Insurance Portability and Accountability Act authorization) before any study-related procedures are performed.
	2. Subject is a healthy man or woman, 18 to 60 years of age, inclusive, who has a body mass index of 18.5 to 29.9 kg/m², inclusive, at Screening.
	3. Subject has normal medical history findings, clinical laboratory results, vital sign measurements, 12-lead electrocardiogram (ECG) results, and physical examination findings at Screening or, if abnormal, the abnormality is not considered clinically significant (as determined and documented by the investigator or designee).
	4. Subject must have a negative test result for alcohol and drugs of abuse at screening and Check-in (Day 0).
	5. Subject has no known or suspected allergies or sensitivities to any components of the sunscreen formulation.
	6. Female subjects must be of nonchildbearing potential or, if they are of childbearing potential, they must: 1) have been strictly abstinent for 1 month before Check-in (Day 0) and agree to remain strictly abstinent for the duration of the study and for at least 1 month after the last application of study drug; OR 2) be practicing 2 highly effective methods of birth control (as determined by the investigator or designee; one of the methods must be a barrier technique) from at least 1 month before Check-in (Day 0) until at least 1 month after the last application of study drug.
	7. Female subjects must not be pregnant or lactating before enrollment in the study.
	8. Male subjects must agree to practice 2 highly effective methods of birth control (as determined by the investigator or designee; one of the methods must be a barrier technique) from at least 1 month before Check-in (Day 0) until at least 1 month after the last application of study drug.
	9. Subject is highly likely (as determined by the investigator) to comply with the protocol-defined procedures and to complete the study.

	Note: subjects with any skin type or skin pigment type may be eligible for the study.
Exclusion Criteria:	Subjects who meet any of the following exclusion criteria will not be eligible to participate in the study:
	1. Subject has broken, irritated, or unhealed skin.
	2. Subject has an active sunburn.
	3. Subject has used a tanning bed in the previous 4 weeks.
	4. Subject has known skin or autoimmune disease(s).
	5. Subject is anemic or has any chronic condition(s) that may impact blood sample collection.
	6. Subject has any underlying disease or surgical or medical condition (e.g., cancer, human immunodeficiency virus [HIV], severe hepatic or renal impairment) that could put the subject at risk or would normally prevent participation in a clinical study.
	7. Subject has known or suspected allergies or sensitivities to any components of the sunscreen formulation.
	8. Subject has clinical laboratory test results (hematology and serum chemistry) at Screening that are outside the reference ranges provided by the clinical laboratory and considered clinically significant by the investigator.
	9. Subject has a positive test result at Screening for HIV 1 or 2 antibody, hepatitis C virus antibodies, or hepatitis B surface antigen.
	10. Subject is unable or unwilling to undergo multiple venipunctures for blood sample collection because of poor tolerability or poor venous access.
	11. Subject has received or applied the topical sunscreen formulations used in the current study, or any other product containing the active ingredients of the topical sunscreen formulations used in the current study, within 7 days before Check-in (Day 0).
	12. Subject has used any personal care product(s) containing any active sunscreen ingredient, such sunscreen products, hand or body moisturizing lotion, makeup or foundation, lip balm, or lipstick, within 7 days before Check-in (Day 0).
	13. Subject is unable or unwilling to tolerate the scent of sunscreen for the duration of the treatment period.
Study Drug, Dosage, and Route of Administration:	
 
Part 1
 
La Roche Posay (Cream), Anthelios SX Daily Moisturizing Cream with Sunscreen, SPF 15 with Mexoryl SX
 

	
 
Hawaiian Tropic (Lotion); Island Sport Ultra-Light High Performance Sunscreen, SPF 50
 

	Neutrogena (Spray), Ultra Sheer Body Mist SPF 45

	Banana Boat (Spray); Sport Performance Coolzone Continuous Spray Sunscreen, SPF 50
	Approximately 2 mg of sunscreen formulation per 1 cm  of body surface will be applied topically 4 times per day for 4 days to approximately 75% of the body surface area.
	Part 2
	Hawaiian Tropic (Lotion); Island Sport Ultra-Light High Performance Sunscreen, SPF 50
	Neutrogena (Aerosol Spray), Ultra Sheer Body Mist SPF 100
	• Supergoop (Non-Aerosol Spray), Sunscreen Mist with Vitamin C SPF 50
	Supergoop (Pump Spray), Sun Defying Sunscreen Oil with Meadowfoam SPF 50
	Approximately 2 mg of sunscreen formulation per 1 cm  of body surface will be applied topically once on Day 1 and 4 times per day (over eight hours) on Days 2-4 to approximately 75% of the body surface area.
Reference Drug, Dosage, and Route of Administration:	Not applicable.

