# 5. Investigational Plan

# 5.1. Study Design

This will be a single clinical study conducted in 2 parts. The duration of study participation will be approximately 37 days for part 1, including a 30-day screening period, a 4-day treatment period (Days 1-4) and subjects leaving the clinic on the morning of Day 7 following completion of scheduled End-of-Study activities. For part 2, the duration of participation will be approximately 51 days, including a 30-day screening period, a 4-day treatment period (Days 1-4) and subjects leaving the clinic on the morning of Day 7. Subjects in part 2 will then return to the clinical for follow-up visits on Days 10, 14 and 21 after which End-of-Study activities will be completed.

#### 5.1.1 Part 1

Part 1 is an open-label, randomized, 4-arm pilot study to evaluate the effects of multiple applications of 4 different topical sunscreen formulations in healthy adult subjects. Each arm will include 6 subjects (3 male and 3 female) with 1 formulation. A total of 24 subjects (12 male and 12 female) from all 4 arms will be admitted to the clinical research unit (CRU) on Day 0.

On the morning of Days 1 through 4, subjects will receive a topical application of the study product at approximately 0900 hours. The study drug will be weighed in advance and applied by a qualified person from the study team. Subjects will then receive 3 more topical applications on the same day at 2, 4, and 6 hours after the first dose.

### 5.1.2 Part 2

Part 2 is an open-label, 4-arm-study to evaluate the pharmacokinetics of avobenzone, oxybenzone, octocrylene, homosalate, octisalate and octinoxate (Part 2 products will not contain ecamsule) after multiple applications of a topical sunscreen formulation in healthy adult subjects. Part 2 will include 48 subjects (24 male and 24 female) and 12 subjects in each arm (6 male and 6 female). One of the formulations in Part 2 will be selected based on the plasma exposure data from the pilot study (Part 1). In addition, 3 new formulations will be added.

On the morning of Days 1 through 4, subjects will receive a topical application of the study product at approximately 0900 hours. The study drug will be weighed in advance and applied by a qualified person from the study team. Subjects will only receive one application on Day 1. On Days 2, 3 and 4, subjects will receive an initial dose and 3 more topical applications on the same day at 2, 4, and 6 hours after the first dose.

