#### 5.1.4 Common Procedures

Details of study visits and study procedures are described in Section 5.6 and Section 5.7, respectively, and the overall Schedule of Events for both parts of the study is presented in Section 10.1.

In both parts of the study, approximately 2 mg of sunscreen per 1 cm² of body surface (calculation per method of Dubois) will be evenly applied 4 times per study day (except for a one-time application on the first day in part 2) to areas of the body typically exposed to the sun: face, ears, neck, torso, arms, and legs (approximately 75% of the body surface area). The antecubital areas will be avoided when applying the sunscreen due to potential contamination of the sites used for intravenous (IV) PK blood sample collection. The topical applications of the study drug will be administered with subjects in swim wear to simulate real world settings as well as for easy application. In addition to swim wear, subjects may wear scrubs in between applications and at other times throughout the day/night. Subjects are required to shower each morning after the first PK blood sample collection (and before the first sunscreen application for that day), but not at other times during the day. And, subjects should not use any personal care products which contain avobenzone, oxybenzone, ecamsule, octocrylene, homosalate, octisalate or octinoxate during the study.

Blood samples (approximately 10 mL per sample) will be collected for determination of avobenzone, oxybenzone, octocrylene, ecamsule, homosalate, octisalate and octinoxate (where applicable) plasma concentrations.

Safety evaluations will include adverse event (AE) monitoring, vital sign measurements, and physical examinations. All AEs reported by the subject or observed by the investigator or CRU staff will be recorded. Any AE reported after the informed consent is signed and before study drug application will be recorded as medical history.

Subjects will remain in the CRU after admission on Day 0 until discharge on the morning of Day 7. In Part 2, subjects will return to the clinic on Day 10, 14 and 21 for follow-up PK sampling (Days 10, 14 and 21) and tape stripping (Days 14).

Subjects are not allowed to use products containing any of the active ingredients from 7 days before check-in until completion of End-of-Study procedures.

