### Across all study days (Primary Endpoint)

• Maximum concentration (observed peak drug concentration) (Cmax)

#### Days 1

- Maximum concentration (observed peak drug concentration) (Cmax)
- Time at which  $C_{max}$  occurs  $(T_{max})$

• AUC from time 0 to the sampling time corresponding to the last quantifiable concentration (Clast) (AUC0-t), calculated by the mixed linear logarithmic trapezoidal method

### Days 2 and 3

- Residual drug concentration (predose level) (Ctrough)
- 3 h post dose concentration

### Day 4

- Elimination rate constant (Kel), obtained by linear regression of the log-linear terminal phase of the concentration-time profile using at least 3 data points, excluding Cmax, otherwise Kel will not be determined. The acceptability criteria for determination of Kel will be a coefficient of regression more than or equal to 0.98.
   When Kel will not be determined, AUC0-inf and t1/2 will not be reported.
- Terminal half-life  $(t_{1/2})$ , calculated using the equation  $\ln 2/k$  after the last study drug application (on Day 4)
- Accumulation ratios, calculated using the following formula:

$$R_1 = AUC_{0-23} Day 4 / AUC_{0-23} Day 1$$

• AUC from time 0 extrapolated to infinity (AUC0-inf), calculated by the mixed linear-logarithmic trapezoidal method as:

$$AUC_{0\text{-inf}} = AUC_{0\text{-t}} + C_{last} / K_{el}$$

When the extrapolation represents more than 20%,  $AUC_{0-inf}$  and  $t_{1/2}$  will not be reported.

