Attachment B. Randomization Schedule

Randomization in this study is unblinded.

After screening, subjects will be randomized to one of 4 treatment sequences in either Part 1 (24 subjects) or Part 2 (48 subjects). Example of treatment codes from the study protocol:

- Treatment sequences of Part 1:
 - A: La Roche Posay (Cream), Anthelios SX Daily Moisturizing Cream with Sunscreen, SPF 15 with Mexoryl SX (6 subjects): Avobenzone (2%), Ecamsule (2%) and Octocrylene (10%)
 - B: Hawaiian Tropic (Lotion); Island Sport Ultra-Light High Performance Sunscreen, SPF 50 (6 subjects): Avobenzone (3%), Oxybenzone (4%) and Octocrylene (6%)
 - C: Neutrogena (Spray), Ultra Sheer Body Mist SPF 45 (6 subjects): Avobenzone (3%), Oxybenzone (6%), Octocrylene (2.35%), Homosalate (15%) and Octisalate (5%)
 - D: Banana Boat (Spray); Sport Performance Coolzone Continuous Spray Sunscreen, SPF 50 (6 subjects): Avobenzone (3%), Oxybenzone (5%) and Octocrylene (10%)

- Treatment sequences of Part 2:
 - E: Hawaiian Tropic (Lotion); Island Sport Ultra-Light High Performance Sunscreen, SPF 50 (12 subjects): Avobenzone (3%), Oxybenzone (4%) and Octocrylene (6%)
 - F: Neutrogena (Aerosol Spray), Ultra Sheer Body Mist SPF 100 (12 subjects): Avobenzone (3%), Oxybenzone (6%), Octocrylene (10%), Homosalate (15%) and Octisalate (5%)
 - G: Supergoop (Non-Aerosol Spray), Sunscreen Mist with Vitamin C SPF 50 (12 subjects): Avobenzone (3%), Octocrylene (10%), Homosalate (10%), Octisalate (5%) and Octinoxate (7.5%)
 - H: Supergoop (Pump Spray), Sun Defying Sunscreen Oil with Meadowfoam SPF 50 (12 subjects): Avobenzone (3%), Homosalate (10%), Octisalate (5%) and Octinoxate (7.5%)

The script performs randomization across treatment groups; all subjects in Part 1 will be studied in 1 cohort (cohort 1) and subjects in part 2 will be studied in 2 cohorts (cohorts 2 and 3).

Treatment schedule

RANDID	PART	COHORT	SEQ
1001	1	1	D
1002	1	1	A
1003	1	1	C
1004	1	1	B

Statistical Analysis Plan**SCR-005: Assessment of the Human Systemic
Absorption of Sunscreen Ingredients**

1005	1	1	D
1006	1	1	B
1007	1	1	A
1008	1	1	C
1009	1	1	C
1010	1	1	B
1011	1	1	A
1012	1	1	D
1013	1	1	B
1014	1	1	A
1015	1	1	D
1016	1	1	C
1017	1	1	B
1018	1	1	A
1019	1	1	C
1020	1	1	D
1021	1	1	A
1022	1	1	D
1023	1	1	C
1024	1	1	B
2001	2	2	G
2002	2	2	E
2003	2	2	F
2004	2	2	H
2005	2	2	E
2006	2	2	G
2007	2	2	F
2008	2	2	H
2009	2	2	G
2010	2	2	E
2011	2	2	H
2012	2	2	F
2013	2	2	F
2014	2	2	G

Statistical Analysis Plan**SCR-005: Assessment of the Human Systemic

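### One synopsis sentence sets the applied amount as 2 mg of active ingredient per cm², while every other statement of it says 2 mg of formulation or of sunscreen; the basis for weighing needs to be reconciled

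*Protocol*

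**What the plan says.** The applied amount is stated in four places in the current protocol.

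- **Synopsis, Study Design, Parts 1 and 2:** "approximately 2 mg of active sunscreen ingredient per 1" cm² of body surface, for both parts.
- **Synopsis, Study Drug, Dosage, and Route of Administration:** "Approximately 2 mg of sunscreen formulation per 1" cm², once under Part 1 and again under Part 2.
- **Section 5.1.4, Common Procedures:** "approximately 2 mg of sunscreen per 1 cm² of body surface". This is the body-text counterpart of the synopsis design sentence, and the word active is absent.
- **Section 5.8.1, Treatments Administered:** the formulation wording of the dosage row, again once per part.

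Sections 5.1.1 and 5.1.2 say how the amount is prepared: "The study drug will be weighed in advance and applied by a qualified person from the study team". They do not restate the basis. The SAP lists label strengths in Attachment B but gives no amount per cm². Neither document offers a conversion between the bases or a rule on which statement takes precedence.

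**The concern.** The 2 mg figure tells the site how much product to weigh out. An amount of active ingredient and an amount of formulation can be the same only if the formulation is all active ingredient, and the protocol's own background says otherwise: "The amount of sunscreen ingredient in a product can vary, but permitted levels can be as high as 15% for some organic active ingredients". One number therefore has two meanings.

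The active-ingredient wording is also incomplete in itself. Each product holds three to five actives, and the sentence does not say whether the 2 mg is their total or one of them.

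What is at stake is a known applied amount. The study describes absorption under maximal-use conditions. Section 5.7.1.4 makes Cmax across all study days the primary endpoint, and SAP section 5 names avobenzone Cmax as the primary outcome. The amount applied is part of what those results describe. Section 9.3.2 lists deviations in study drug administration among those that may be significant, and a deviation cannot be judged against two bases.

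**Working it through.** There is no stated figure to reproduce: the sample size is empirical, and neither document calculates a mass. The check compares the wordings and then shows what the difference would mean under one assumed reading.

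**Inputs.** The 2 mg per cm² comes from the four places above. Active content *s* is the sum of the label percentages in SAP Attachment B.

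**Formulas.**
- Formulation reading: product applied = 2 mg/cm²; total active applied = 2 × *s*.
- Total-active reading (assumed): product applied = 2 / *s*; factor over the formulation reading = 1 / *s*.

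| Arm | Sum of actives (%) | Active applied, formulation reading (mg/cm²) | Product applied, total-active reading (mg/cm²) | Factor |
|---|---|---|---|---|
| A | 2 + 2 + 10 = 14 | 0.28 | 14.29 | 7.14 |
| B and E | 3 + 4 + 6 = 13 | 0.26 | 15.38 | 7.69 |
| C | 3 + 6 + 2.35 + 15 + 5 = 31.35 | 0.627 | 6.38 | 3.19 |
| D | 3 + 5 + 10 = 18 | 0.36 | 11.11 | 5.56 |
| F | 3 + 6 + 10 + 15 + 5 = 39 | 0.78 | 5.13 | 2.56 |
| G | 3 + 10 + 10 + 5 + 7.5 = 35.5 | 0.71 | 5.63 | 2.82 |
| H | 3 + 10 + 5 + 7.5 = 25.5 | 0.51 | 7.84 | 3.92 |

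No product comes near 100% active, so the two bases never coincide.

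**Between arms, at equal body surface.** On the formulation reading, product mass is the same in every arm (ratio 1.0). On the total-active reading:
- Part 1, largest over smallest: B over C = 31.35 / 13 = 2.41.
- Part 2, largest over smallest: E over F = 39 / 13 = 3.00.

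**Why these figures are not a bound.** If a single active were meant, the factor would be 100 divided by that active's percentage. For avobenzone, the only active present in all seven products, this is 100 / 2 = 50 in A and 100 / 3 = 33.3 in the rest. For octocrylene in C it is 100 / 2.35 = 42.6. The synopsis sentence does not choose among these, so the table illustrates one reading and does not limit the ambiguity.

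**The case against.** The strongest reply is that the rest of the protocol leaves little doubt in practice. The active-ingredient wording appears once. Against it stand five statements: two in the dosage row, two in section 5.8.1, which is the section on treatments administered, and one in section 5.1.4. What is weighed is called the study drug, and section 5.8.3 identifies the formulations as commercially available products. On this view the sentence is a drafting slip, and quoting multiples of product mass makes an editorial error look like a dosing hazard.

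Much of this stands. The isolation of the wording makes misapplication less likely, and the single-active factors of 33 to 50 are not a practical scenario. The analyses are descriptive, with no formal test between arms, so the 2.4-fold and 3.0-fold ratios do not feed into any planned comparison.

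It does not remove the contradiction. One of the formulation statements sits in the same synopsis as the odd sentence, so a synopsis-versus-body rule would not settle the matter even if the protocol had one. The sentence concerns the amount to be applied, and is not background text.

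A reader might also infer three stronger things, none of which the documents support:

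- **Subjects receive the wrong amount.** Nothing shows how the site weighs product.
- **Cmax would shift in proportion to applied mass.** The documents give no relation between applied amount and plasma concentration.
- **The choice of product carried from Part 1 is in doubt.** The current protocol already names that product in its Part 2 lists, and correcting the wording does not reopen the choice.

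**Conclusion.** The inconsistency is real, is in current text and should be fixed. The protocol states the 2 mg on bases that cannot agree, given total active content of 13% to 39%. If total actives were meant, product mass per application would be 2.6 to 7.7 times that of the formulation reading, with a different factor for each distinct product. Applied mass would then differ between arms by up to 2.4-fold in Part 1 and 3.0-fold in Part 2. These sizes rest on the Attachment B label strengths, on equal body surface for the arm ratios, and on an assumed reading of a sentence that does not define its own basis.

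The point goes no further than the wording. It does not say which basis is intended, and sample size, product selection and the planned summaries are unaffected.

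A separate and minor item is held with low confidence because the page is poorly extracted. The Appendix A footnote on study drug administration lists an application at about 0900 and further ones 2, 4 and 6 hours later. It does not mention the single application on Day 1 of Part 2 that the synopsis and sections 5.1.2, 5.1.4, 5.6.3.2 and 5.8.1 set out.

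**What to change.** Reconcile the synopsis design text for Parts 1 and 2, the synopsis dosage row, section 5.1.4 and section 5.8.1 to one explicitly stated basis for the 2 mg, and notify the site. The sponsor decides which basis is meant. If that basis is active ingredient, the text must also say whether it is total actives or a named one.

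Separately, check the Appendix A administration footnote against the original page and, if it reads as extracted, reconcile it with the synopsis and sections 5.1.2, 5.1.4, 5.6.3.2 and 5.8.1 on the number of Part 2 Day 1 applications.

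The cost is a protocol wording correction, with the IRB review that section 9.3.1 requires for amendments, and a site notice. Sample size, product selection and analysis do not change.
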